Below is a detailed description of all techniques and measurements to be utilized and/or obtained, as well as a complete description of the experimental protocol (see schematic illustration below). First, all participants will complete an in-person screening/familiarization visit (~1.5 hours) to determine eligibility. Thereafter, each participant will complete two 15-day measurement bursts (hereafter referred to as "testing cycles"). Micro-longitudinal measurement burst/testing cycle designs consist of repeated sequences of closely spaced assessments that provide multiple time scales, allowing for the examination of processes unfolding within an individual over short time periods (e.g., days) as well as how these change over longer time intervals (e.g., months). Each 15-day testing cycle consists of 1) an ambulatory assessment of daily stress processes and cognitive function for 14 consecutive days (~2-3 hours in total), 2) daily wrist accelerometry for 14

consecutive days (no additional time burden), 3) daily saliva collection for 4 consecutive days (~1 hour in total), and 4) an experimental visit to assess vascular endothelial function (~6 hours). The two cycles will be separated by ~3-6 months; the lack of standardization of the timing between cycles is purposeful, as it will allow us to begin to more precisely disentangle the temporal patterning of the proposed relations both within- and between-subjects. This protocol is illustrated below:

Pre-Screening: Initial Interview/Survey to Determine Eligibility

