4. Participants will store these samples in their refrigerator and will return them to the researchers at the experimental visit. The samples will then be frozen and stored until analysis.

Experimental Laboratory Visit (Day 15)

1. Vital signs (oral temperature, heart rate, and blood pressure) are measured upon arrival to the lab. Women who are premenopausal submit urine for a pregnancy test if they have not been tested within the 2 weeks prior to the experimental visit.
2. Participants complete the Patient Health Questionnaire-9 (PHQ-9) to assess depressive symptom severity. The PHQ-9 has 9 questions (see attached document "PHQ-9"). Each question is scored on a Likert scale. The total score can range from 0 to 27.
3. Participants complete the Generalized Anxiety Disorder-7 (GAD-7) item scale to assess anxiety symptom severity. The GAD-7 has 7 questions (see attached document "GAD-7"). Each question is scored on a Likert scale. The total score can range from 0 to 21.
4. Participants complete the Big Five Inventory to assess neuroticism, openness to experience, conscientiousness, extraversion, and agreeableness (see attached document "Big Five Inventory"). Participants are provided with 44 personality characteristics that may or may not apply to them. On a Likert scale (strongly disagree to strongly agree), participants rate the extent to which they agree or disagree with each statement.
5. Participants complete the Life Events Checklist to assess exposure to any major stressful life events (episodic in nature, with identifiable onset) and other sources of chronic and persistent psychosocial stress (stressors that are demanding, distressing, and ongoing) over the past 12

months (see attached document “Life Events Checklist”).

6. Participants complete the Pittsburgh Sleep Quality Index (see attached document “PSQI”), a 10-item measure of sleep quality and sleep habits.
7. Participants complete the International Physical Activity Questionnaire to assess habitual physical activity (IPAQ; see attached document “IPAQ”).

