 - Then we insert a thin needle into the skin at each entry mark. The needle's tip travels between the layers of skin for ~2.5 cm (1 inch) and exits the skin at the matching exit-mark.
 - We thread the microdialysis tubing through the needle and then withdraw the needle leaving the tubing in the skin.
 - We prepare up to 3 microdialysis sites.
 - Any hyperemia related to the insertion subsides in about 60 minutes. During this time lactated Ringers or a site-specific pharmacological agent listed below perfuses the microdialysis tubing:
 - lactated Ringers
 - lactated Ringers + mitoTempol
 - lactated Ringers + Tempol
- We use laser Doppler flowmetry to measure cutaneous microvascular blood flow:
 - We tape thin fiber optic laser Doppler flowmeter probes and their holders on the forearm over each microdialysis site.
 - The thin probe measures skin blood flow with a weak laser light. We measure skin blood flow continuously throughout the experiment.
 - We can control the temperature of the holders.
- At the start of the experiment, we obtain ~20 minutes of baseline measurements. During this time, the temperature holders are set to thermoneutrality (33°C/91.4°F).
- Then, we increase the temperature of the holders to 42°C/107°F (0.1°C/sec).
- After skin blood flow stabilizes (~45 min), we switch the fluid in all probes to L-NAME.
- After skin blood flow stabilizes a second time (~45 min), we switch the fluid in all probes to sodium nitroprusside. At the same time, we warm the probe's holder to 43°C (108°F) for ~30 minutes to cause maximal dilation.
 - If a participant is asked to repeat this procedure, it will occur during a separate laboratory visit.

13. At the conclusion of the experiment, we remove the microdialysis tubing from the skin and place sterile bandages over the site. If the subject desires, we place a bag of ice on the site for 10 min to reduce bruising that may occur. The investigators complete an assessment of each microdialysis site and complete the Microdialysis Discharge Form.

14. We measure blood pressure and heart rate before the subject leaves the laboratory.

Subject Participation: A subject may decide not to participate in a particular experimental measurement or procedure or may decide not to participate in the second testing cycle; therefore, in these situations, this portion of the protocol will not be completed. However, all other measurements and procedures will be performed. This will not affect the scientific value of the

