To ensure robust and unbiased results, we will use defined protocols for including/excluding, enrolling, and testing subjects. Multiple experimental controls and orthogonal approaches will be used, and relevant psychobiological variables are factored into the research design and analyses. Data analysis will be blinded, when applicable and to the extent that this is possible, and performed by two independent investigators.

All statistical analyses will be performed with SAS. Descriptive statistics will be calculated for all data. Prior to all analyses, we will examine the distributions of continuous variables for departures from normality, separately and in combination, for possible violations of assumptions (e.g., multicollinearity). For continuous variables, the mean and standard deviation will be calculated. Medians and interquartile ranges will be calculated if a continuous variable is skewed. The 95% confidence interval (CI) will be provided as appropriate. Model fit diagnostics will be used to evaluate the appropriateness of linear modeling for primary hypotheses. If appropriate, log transformation may be performed. Statistical significance will be accepted at $p < 0.05$. The analyses will be based on a variety of statistical techniques. Most will focus on the use of multilevel modeling and multilevel structural equation modeling which allows the appropriate analysis of data

that are nested (that is, observations come from the same individual over time).

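### Does leaving the 3-6 month gap between the two testing cycles unstandardised call for a change, given that each person has only one gap?

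*Combined protocol and SAP*

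**What the plan says.** The design overview in section 6 states that "each participant will complete two 15-day measurement bursts" and that "The two cycles will be separated by ~3-6 months". It presents the open interval as deliberate: "the lack of standardization of the timing between cycles is purposeful, as it will allow us to begin to more precisely disentangle". What is to be separated in this way is described as "the temporal patterning of the proposed relations both within- and between-subjects". The same paragraph describes burst designs in general as showing processes over days "as well as how these change over longer time intervals (e.g., months").

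Under Subject Participation in section 6, a participant "may decide not to participate in the second testing cycle". Under Experimental Laboratory Visit (Day 15), which occurs in each cycle, "Participants complete the Patient Health Questionnaire-9 (PHQ-9) to assess depressive symptom severity".

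The analysis answer in section 10 (Data) is short. It names multilevel models and multilevel structural equation models, and says that "relevant psychobiological variables are factored into the research design and analyses". It lists no outcome, group, cycle, gap or covariate term for any aim. Section 7 plans 60 healthy adults, 60 unmedicated adults with MDD and 30 SSRI-treated adults with MDD. Section 6 describes only the first two groups.

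**The concern.** The plan gives up a standard interval in return for a stated scientific benefit, part of which is described as within-subject. With two cycles, gap length is a fixed characteristic of the person. The within-person information in the study, namely the 14 days of assessments in each cycle and the change from cycle 1 to cycle 2, would be the same with a fixed gap. What a varied gap adds is a way to separate elapsed time from simply being in the second cycle. A retest effect is plausible, because the same cognitive tasks recur twice a day in both cycles.

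If that separation rests on comparing people with short and long gaps, it matters how a gap comes about. Were gaps to follow symptoms, availability or season, a gap effect could be produced by the kind of person who returns late. The plan states no allocation rule and no adjustment, so one purpose it gives for leaving the timing open looks unsupported.

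**Working it through.** The plan gives no power, precision or identification figure for the gap, so there is none to reproduce. Three checks were made.

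**1. What can be estimated.** Take 120 people (60 + 60, the two groups in section 6) and two cycles.

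| Model | Data per cycle | Gap | Rank / parameters |
|---|---|---|---|
| Person-specific baseline, cycle and elapsed time | one row | varied or fixed | 240 / 360 |
| Person baselines, one pooled cycle effect, one pooled elapsed-time effect | one row | varied | 122 / 122 |
| Same pooled model | one row | fixed | 121 / 122 |
| Person-specific model | 14 daily rows | varied or fixed | 360 / 360 |

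The counts are 3 × 120 = 360 parameters, 2 × 120 = 240 rows, and 120 + 2 = 122 pooled parameters. For outcomes measured once per cycle, such as the Day 15 vascular measures, person-specific separation is impossible. Pooled separation becomes possible only because gaps differ between people. For daily outcomes all 360 parameters are estimable, but this comes from the days within a cycle plus an assumption of linear time, and a fixed gap gives it too. Varying the gap therefore helps the pooled model for once-per-cycle outcomes, through between-person contrasts.

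**2. How far confounding could mislead.** Assume no true gap effect, n = 120, and a severity trait correlated *a* with gap and *b* with between-cycle change. None of these correlations is in the documents. The spurious gap-change correlation is *a* × *b*. At 0.3 and 0.3 it is 0.09; on the Fisher scale 0.0902 × √117 = 0.976, which gives a rejection rate of about 16%, in line with the simulation (20,000 runs per case, two-sided 0.05):

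| *a* / *b* | Unadjusted | Adjusted, severity measured at assumed reliability 0.8 |
|---|---|---|
| 0 / 0.3 | 5.1% | 5.2% |
| 0.1 / 0.3 | 6.2% | 5.0% |
| 0.2 / 0.3 | 9.9% | 5.4% |
| 0.3 / 0.3 | 16.6% | 5.5% |
| 0.3 / 0.5 | 37.6% | 6.8% |
| 0.5 / 0.5 | 79.6% | 10.3% |

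The unadjusted column describes a test that the plan does not propose. PHQ-9 is collected at each experimental visit, so severity can be adjusted for. Unmeasured causes cannot.

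**3. What a gap analysis could detect.** Suppose gaps were set at random to 3, 4, 5 or 6 months. Their SD is √[(2.25 + 0.25 + 0.25 + 2.25)/4] = 1.118. For 80% power at two-sided 0.05, the detectable correlation is r = tanh[(1.960 + 0.842)/√(n − 3)], and the 3-versus-6-month contrast is 3r/1.118 in SDs of change.

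| n | r | 3 vs 6 months |
|---|---|---|
| 150 (all groups in section 7) | 0.227 | 0.61 SD |
| 120 | 0.253 | 0.68 SD |
| 96 (120 less an assumed 20% who skip cycle 2) | 0.283 | 0.76 SD |
| 60 (one group) | 0.355 | 0.95 SD |

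Random allocation would remove the confounding, but the analysis could still detect only fairly large differences.

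**The case for a change.** The strongest case for a change is one of timing and cost. Gaps can be randomised only before cycle 2 is scheduled, and the reasons for a gap are hard to reconstruct later. A short allocation list within the existing range needs no extra visits. Without it, the plan forgoes standard timing and secures nothing in exchange.

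Part of this stands. The information that a varied gap adds for once-per-cycle outcomes is between-person. The sentence in section 6 is loosely worded on that point, and nothing in the visible text says how gaps arise. The rest carries less weight:

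- The sentence promises no person-specific gap effect. It can fairly be read as saying that the stress-biology relations will be studied within and between people in pooled multilevel models, and that varied timing begins to help. The first check agrees with that reading.
- The missing gap term is not peculiar to the gap, since the analysis answer names no model terms for any aim.
- Nothing in the documents suggests that gaps track severity, and a scheduling detail in the study schematic, which is not shown, cannot be excluded.
- Fixing target gaps adds scheduling constraints and might reduce return for a cycle that participants are free to decline. That would put cycle 2 data at risk for a purpose on which no aim depends.

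**Conclusion.** No change to the plan is needed. It is correct that each person contributes one gap, and that gap effects on once-per-cycle outcomes rest on comparisons between people. But Aims 1-3 concern links between daily stress and inflammatory, redox, vascular and cognitive measures, and none turns on gap length. Rewording the rationale would alter no result. Randomising gaps is a fair trade-off for the investigators to weigh, not a correction.

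The omission is one that analysts can fill sensibly. Dated records, such as the dates written down for saliva samples, give the actual gap. Any elapsed-time analysis can be adjusted for cycle 1 PHQ-9 and season, and reported as exploratory, between-person and open to unmeasured confounding. Its reach is limited: detectable contrasts run from 0.61 SD (n = 150) to 0.95 SD (n = 60) between 3 and 6 months. Those figures assume random, evenly spread gaps, and all but the n = 96 row assume full return for cycle 2. The false-positive figures rest wholly on assumed correlations and an assumed reliability of 0.8. The conclusion would differ if a confirmatory claim about elapsed time were later made; the plan makes none.

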 - Participants will receive detailed instructions on how to access and complete the daily surveys and will practice using the Gorilla experiment builder on their personal mobile device (this will be used to administer the daily cognitive tasks described below) and/or the Metricwire mobile app on a laboratory-provided smartphone. Depending on scheduling of "testing cycle #1" and the availability of associated equipment, some participants may be asked to complete an additional, but very brief (<5 min), in-person visit to pick up this equipment prior to Day 1 of the ambulatory assessments. Participants may also be asked to complete this brief in-person prior to Day 1 of "testing cycle #2."
 - Participants will be fitted for a wrist accelerometer (MotionLogger, Actigraph) that will be

worn every day during the 14-day assessment period and used to objectively measure daily sleep and activity/sedentary behaviors. They will also be instructed regarding its use (described below). Depending on scheduling of “testing cycle #1” and the availability of associated equipment, some participants may be asked to complete an additional, but very brief (<5 min), in-person visit to pick up this equipment prior to Day 1 of the ambulatory assessments. All participants will also be asked to complete this brief in-person prior to Day 1 of “testing cycle #2.”

- Participants will also be instructed in and provided a home saliva collection kit (described below). Depending on scheduling of “testing cycle #1”, some participants may be asked to complete an additional, but very brief (<5 min), in-person visit to pick up this equipment prior to Day 1 of the ambulatory assessments. All participants will also be asked to complete this brief in-person prior to Day 1 of “testing cycle #2.”

Screening ‘failures’ will be tracked for date of screening and reason for ineligibility/exclusion; however, if not enrolled, all screening information and data will be de-identified and destroyed.

Ambulatory Assessment of Daily Stress Processes and Cognitive Function (Days 1-14)

Note: Participants will complete the ambulatory assessments described below using either Qualtrics (accessed via the The Pennsylvania State University institutional contract but completed using any of their personal devices with internet connectivity; e.g., smartphone, tablet, etc.) or the Metricwire mobile app on a laboratory-provided smartphone (see attached document “Metricwire Instructions”).

1. Participants are familiarized with the organization, flow, and types of questions in the ambulatory assessments prior to participation. They will practice using the Gorilla experiment builder on their personal mobile device at the screening/familiarization laboratory visit.
2. Participants will complete a morning assessment and an evening assessment each day for 14 consecutive days (Days 1-14). Beginning on the first day of the ambulatory assessments, participants will receive pre-scheduled alert notifications via text/email twice per day (~9a and ~7p), prompting them to complete a short morning survey (2-3 min) and a slightly longer evening survey (5-7 min). These notifications are programmed and generated by Qualtrics or Metricwire and include direct access to the associated survey.
3. The morning survey asks questions about sleep, morning outlook, and anticipatory stress and positive experiences (see attached document “Daily Stress Script”). The investigators do not monitor answers to these surveys on a daily basis; instead, these data are compiled at study completion.
4. The evening survey asks questions about the participant’s daily experiences (stressors, mood, physical symptoms), and memory lapses (see attached document “Daily Stress Script”). The investigators do not monitor answers to these surveys on a daily basis; instead, these data are compiled at study completion.
5. Within both the morning and evening surveys, some questions will ask participants to select a single option, some questions will ask participants to check the boxes of as many options as are relevant to their answer, some questions involve drop down menus, and some questions involve a slider scale.
6. After each survey, participants will complete three brief objective cognitive tasks or “brain games” (see attached document “Daily Cognition Tasks”). The cognitive tasks will be administered using either Gorilla experiment builder (accessed via a link at the end of each Qualtrics survey) or directly within the Metricwire mobile app. If using Qualtrics, participants will click on the link to directly access the tasks in Gorilla experiment builder. This link will include a unique identifier connecting the participant’s survey results to their Gorilla task results. Direction screens are provided before each game.
 - In the *paired associates* task, participants see words paired with numbers and have to recall the number paired with each word.

- In the *forward number span* task, participants see a series of numbers (from 3-7 digits long) and have to enter the numbers in the order they appeared. In the *backward number span* task, participants again see a series of numbers (from 2-6 digits long) and have to enter the numbers in reverse order.
- In the *spatial n-back* task, participants see 4 squares that change color. When the same square changes color twice in a row, they have to click a button on the screen.

7. During the same 14 days, participants will also wear an accelerometer watch (MotionLogger Actigraph) on their non-dominant wrist during all waking and sleeping hours to objectively assess sleep and activity/sedentary behavior. They will be instructed in its use, including removal of the wristwatch for any water-based activities (e.g., showering, bathing, swimming, etc.).

8. On Day 15 (i.e., the day immediately after completion of the 14-day ambulatory assessments), participants will return to the laboratory for the experimental visit. They will return the accelerometer at this visit.

Daily Saliva Collection (Days 3-6)

1. Participants will be asked to provide saliva samples for 4 consecutive days, beginning on Day 3 of the ambulatory assessments (described above) and continuing until Day 6. These samples will be tested for stress hormones (e.g., cortisol) and indices of mitochondrial function (e.g., cell-free mitochondrial DNA). The home saliva collection kit contains collection instructions (see attached document "Saliva Collection Instructions"), all collection materials, and a saliva collection worksheet (see attached document "Saliva Collection Worksheet") and is provided in a small portable cooler for ease of transportation and storage. All samples are coded and do not contain personal identifiable information.
2. Participants will collect their saliva 4 times per day (once upon awakening and before getting out of bed, once 30 minutes after getting out of bed, once at lunchtime, and once in the evening). Participants will record the date and time of each collected saliva sample. They will collect a total of 16 saliva samples over the 4-day sampling timeframe.
3. To collect saliva, participants will use a salivette, which includes a cotton swab that they will put in their mouth for 2 minutes. After 2 minutes, they will place the cotton swab back in the salivette tube.
4. Participants will store these samples in their refrigerator and will return them to the researchers at the experimental visit. The samples will then be frozen and stored until analysis.

Experimental Laboratory Visit (Day 15)

1. Vital signs (oral temperature, heart rate, and blood pressure) are measured upon arrival to the lab. Women who are premenopausal submit urine for a pregnancy test if they have not been tested within the 2 weeks prior to the experimental visit.
2. Participants complete the Patient Health Questionnaire-9 (PHQ-9) to assess depressive symptom severity. The PHQ-9 has 9 questions (see attached document "PHQ-9"). Each question is scored on a Likert scale. The total score can range from 0 to 27.
3. Participants complete the Generalized Anxiety Disorder-7 (GAD-7) item scale to assess anxiety symptom severity. The GAD-7 has 7 questions (see attached document "GAD-7"). Each question is scored on a Likert scale. The total score can range from 0 to 21.
4. Participants complete the Big Five Inventory to assess neuroticism, openness to experience, conscientiousness, extraversion, and agreeableness (see attached document "Big Five Inventory"). Participants are provided with 44 personality characteristics that may or may not apply to them. On a Likert scale (strongly disagree to strongly agree), participants rate the extent to which they agree or disagree with each statement.
5. Participants complete the Life Events Checklist to assess exposure to any major stressful life events (episodic in nature, with identifiable onset) and other sources of chronic and persistent psychosocial stress (stressors that are demanding, distressing, and ongoing) over the past 12

months (see attached document “Life Events Checklist”).

6. Participants complete the Pittsburgh Sleep Quality Index (see attached document “PSQI”), a 10-item measure of sleep quality and sleep habits.
7. Participants complete the International Physical Activity Questionnaire to assess habitual physical activity (IPAQ; see attached document “IPAQ”).
8. A research nurse will insert an intravenous (IV) catheter into an antecubital vein of the dominant arm to obtain a blood sample (100 ml/~6.7 tbsp). The researchers do not perform genetic analyses on the blood, nor do they look for the presence of disease (e.g., HIV). Blood samples will be stored in a -80°C freezer (in the laboratory space designated for freezers and refrigerators on the 2nd floor of the Tower at STAR) to allow for batched analyses of substances of interest [inflammatory cytokines, indices of redox balance, peripheral blood mononuclear cells, stress hormones, and sex hormones (estradiol, progesterone, follicle stimulating hormone, luteinizing hormone, and testosterone)] to avoid variability. All samples will be coded with a unique code for each subject. The code-key will be kept in the PI’s lab in a locked cabinet. Only PI and authorized personnel will have access to the file. No other students or faculty will have access. After successful analysis, blood will be discarded into a container labelled with a biohazard sign and stored in secondary waste containers.
9. A research nurse will also perform an endothelial cell biopsy, during which they will collect some cells from the walls of the vein. Two sterile J-wires will be inserted through the IV catheter and gently moved back-and-forth inside the blood vessel. One wire is used at a time. After removal, the wires are transferred to a conical tube containing endothelial dissociation buffer. The cells are rinsed, recovered by centrifugation, and then fixed to coverslips and stored in a -80°C freezer (in the laboratory space designated for freezers and refrigerators on the 2nd floor of the Tower at STAR) to allow for batched analyses of proteins that regulate vascular function and redox balance. All samples will be coded with a unique code for each subject. The code-key will be kept in the PI’s lab in a locked cabinet. Only PI and authorized personnel will have access to the file. No other students or faculty will have access.
10. Flow-mediated dilation (FMD) of the brachial artery to assess peripheral vascular function. To provide the most flexibility to participants in terms of time constraints regarding scheduling, this procedure may occur at either the screening visit or the experimental visit. During this procedure:
 - We tape 3-5 ECG leads to the chest to measure heart rate throughout the experiment (BioAmp, AD Instruments).
 - A blood pressure cuff will be wrapped around the upper arm to obtain blood pressure via a standard automated oscillometric device (BP Monitor, Welch-Allyn). In addition, beat-by-beat blood pressure will be obtained via finger photoplethysmography (NOVA, Finapres). Blood pressure is measured continuously throughout the experiment.
 - We place a small cuff around the forearm, just below the elbow.
 - Above the elbow, we use a Doppler ultrasound probe covered in ultrasound gel to image the brachial artery. The ultrasound measures blood vessel size and blood velocity.
 - After a 3-minute resting measurement, we tightly inflate the cuff for 5 minutes to occlude blood flow to the forearm.
 - After the cuff deflates, we continue to image the artery for ~5 minutes. We may repeat this measure several times.
11. Pulse wave analysis (PWA) and pulse wave velocity (PWV) to assess arterial stiffness. To measure PWA, a standard blood pressure cuff is placed on the subject’s upper arm. The cuff will inflate/deflate to determine brachial artery blood pressure; after 5 seconds, the cuff will inflate again and automatically capture the PWA waveform. To measure PWV, a blood pressure cuff is placed on the subject’s upper leg. A pen-like probe (applanation tonometer) will be placed against the skin over the carotid artery to continuously measure the pulse wave while the blood pressure cuff on the upper leg is inflated and then deflated. To provide the most flexibility to participants in terms of time constraints regarding scheduling, this procedure

may occur at either the screening visit or the experimental visit.

12. Intradermal Microdialysis to assess the mechanistic regulation of microvascular function.

During this procedure:

- We tape 3-5 ECG leads to the chest and abdomen to measure heart rate throughout the experiment.
- A blood pressure cuff will be wrapped around the upper arm to obtain blood pressure via a standard automated oscillometric device. Blood pressure is measured repeatedly throughout the experiment.
- We insert microdialysis probes:
 - We place a tight band around the non-dominant forearm so we can visualize veins.
 - For each microdialysis site, we make pairs of pen-marks on the arm ~2.5 cm (1 inch) apart and away from veins. We remove the tight band. The microdialysis tubing enters and exits the skin at the marks.
 - We clean the arm with povidone iodine and alcohol and place an ice bag on the site for 5 minutes to numb the skin.
 - Then we insert a thin needle into the skin at each entry mark. The needle's tip travels between the layers of skin for ~2.5 cm (1 inch) and exits the skin at the matching exit-mark.
 - We thread the microdialysis tubing through the needle and then withdraw the needle leaving the tubing in the skin.
 - We prepare up to 3 microdialysis sites.
 - Any hyperemia related to the insertion subsides in about 60 minutes. During this time lactated Ringers or a site-specific pharmacological agent listed below perfuses the microdialysis tubing:
 - lactated Ringers
 - lactated Ringers + mitoTempol
 - lactated Ringers + Tempol
- We use laser Doppler flowmetry to measure cutaneous microvascular blood flow:
 - We tape thin fiber optic laser Doppler flowmeter probes and their holders on the forearm over each microdialysis site.
 - The thin probe measures skin blood flow with a weak laser light. We measure skin blood flow continuously throughout the experiment.
 - We can control the temperature of the holders.
- At the start of the experiment, we obtain ~20 minutes of baseline measurements. During this time, the temperature holders are set to thermoneutrality (33°C/91.4°F).
- Then, we increase the temperature of the holders to 42°C/107°F (0.1°C/sec).
- After skin blood flow stabilizes (~45 min), we switch the fluid in all probes to L-NAME.
- After skin blood flow stabilizes a second time (~45 min), we switch the fluid in all probes to sodium nitroprusside. At the same time, we warm the probe's holder to 43°C (108°F) for ~30 minutes to cause maximal dilation.
 - If a participant is asked to repeat this procedure, it will occur during a separate laboratory visit.

13. At the conclusion of the experiment, we remove the microdialysis tubing from the skin and place sterile bandages over the site. If the subject desires, we place a bag of ice on the site for 10 min to reduce bruising that may occur. The investigators complete an assessment of each microdialysis site and complete the Microdialysis Discharge Form.

14. We measure blood pressure and heart rate before the subject leaves the laboratory.

Subject Participation: A subject may decide not to participate in a particular experimental measurement or procedure or may decide not to participate in the second testing cycle; therefore, in these situations, this portion of the protocol will not be completed. However, all other measurements and procedures will be performed. This will not affect the scientific value of the

subject's participation, as each experimental measurement and procedure provides important and, in most cases, independent information.

Pharmacological Agents: *The chemicals used for intradermal microdialysis in this study are scientific tools, some of which are not FDA-approved dispensable drugs, and they do not have expiration dates. We purchase most of these chemicals in solid form. The chemicals are stable for years when stored according to manufacturer's instructions. Nonetheless, we purchase most of the chemicals in small vials that we typically exhaust within one to several weeks. Once mixed, we use stock solutions of the drugs within a week if stored in the refrigerator. We use solutions within 6 months if they are frozen. Final dilutions of solutions prepared for an experiment are used within a couple of minutes or hours of preparation. All pharmacological agents are prepared immediately prior to use and wrapped in foil to prevent photodegradation.*

All proposed investigational agents have been previously used in human subjects research via intradermal microdialysis.

- Lactated Ringers
 - Role: vehicle control for other investigational substances
 - Form: liquid
 - Source: VWR, Moore Medical, McKesson
- N^G-nitro-L-arginine methyl ester (L-NAME)
 - Role: analog to the amino acid L-arginine; non-specific inhibitor of nitric oxide synthase; prevents blood vessels from dilating
 - Form: powder
 - Source: Calbiochem, EMD Millipore, Tocris
 - Concentration: 15 mM
- mitoTempol
 - Role: scavenger of mitochondrial-derived superoxide
 - Form: powder
 - Source: Sigma-Aldrich
 - Concentration: 1 mM
- Tempol
 - Role: non-specific scavenger of superoxide
 - Form: powder
 - Source: Sigma-Aldrich
 - Concentration: 10 μ M
- Sodium Nitroprusside
 - Role: nitric oxide donor; causes maximal endothelium-independent dilation of blood vessels
 - Form: powder
 - Source: USP
 - Concentration: \leq 100 mM

